658 *randomize a subject until he/she is convinced that the subject/parent will accept assignment to either of*
659 *the two groups.*

660
661 **3.4 Procedures for the RT-CGM Group**

662 The RT-CGM provided at enrollment will be unblinded and the subject will be provided with sensors.
663 The subject will be instructed to use the RT-CGM on a daily basis and will be instructed in the use of the

664 device including calibration of the device using a study HGM and downloading the device (if the subject
665 has a home computer). Those with email access will be asked to email the downloaded data to the clinical
666 center before each scheduled phone call.

667
668 The subject (or parent for minors) will be observed placing the sensor. A guide booklet will be provided
669 for the subject to take home. The subject will be instructed to contact the site staff if any appreciable skin
670 reaction occurs.

671
672 During the visit, the RT-CGM, insulin pump (if the subject uses an insulin pump), and HGM data from
673 the pre-randomization visit week will be reviewed with the subject. The subjects will be provided with
674 algorithms to use to make changes to the diabetes management based on the data from the RT-CGM and
675 HGM.

676
677 **3.5 Procedures for the Control Group**

678 Subjects in the Control Group will have changes made in the insulin dosing based on the HbA1c and the
679 HGM data downloaded at this visit, and the investigator's prior experience in treating the subject.

680
681 Subjects will be provided with a HGM and test strips and will be asked to perform at least 4 fingerstick
682 blood glucose measurements per day.

683
684 The subjects will be provided with algorithms to use to modify diabetes management based on the HGM
685 glucose readings.

686
687 Subjects with a home computer will be provided with the software to download the HGM and will be
688 asked to do so weekly. Those subjects with email access will be asked to email the downloaded data to
689 the clinical center prior to each scheduled phone call.

690
691 **3.6 HbA1c**

692 For randomized subjects, a blood sample will be drawn to send to the central laboratory at the University
693 of Minnesota for the baseline HbA1c determination. The HbA1c will also be measured using the
694 DCA2000 at this visit.

695

CHAPTER 4
RANDOMIZED TRIAL PHASE

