338 events (such as confirmed symptomatic episodes in which assistance was not needed) probably
339 would be biased against the RT-CGM group, since the use of the RT-CGM is likely to identify
340 more events merely because the glucose level is known. Therefore, this cohort of subjects will
341 be included as a secondary pilot study to explore outcomes that could be appropriate to use to
342 evaluate the value of RT-CGM in subjects with HbA1c in the excellent range.
343

344 **1.6.1 Summary of Design of Randomized Trial**

345 **A. Major Eligibility Criteria**

- 346 • Clinical diagnosis of T1D
- 347 • Age ≥ 8 years
- 348 • Insulin regimen includes either an insulin pump or multiple daily injections
349

350 **B. Sample Size**

351 The primary study (HbA1c $\geq 7.0\%$) will include a minimum of 330 subjects, with approximately 110 in
352 each of three age groups of 8 to <15 years old, 15 to <25 years old, and ≥ 25 years old. Depending on
353 the results of an interim analysis (see section 9.1.3) this may be increased up to 450 subjects.

354

355 The secondary study (HbA1c <7.0%) will include a minimum of 120 subjects, with approximately 40
356 in each of three age groups of 8 to <15 years old, 15 to <25 years old, and \geq 25 years old. If the goal of
357 120 subjects is reached prior to completion of recruitment of the primary cohort, recruitment may be
358 continued up to 240 subjects.

359

360 Enrollment will include approximately 50% of subjects using an insulin pump and approximately 50%
361 of subjects using multiple daily injections of insulin (at least 3 shots per day).

362 **C. Treatment Groups**

363 Subjects will be randomly assigned with equal probability to the following 2 groups:

- 364 • RT-CGM for 12 months
- 365 • Control Group using HGM monitoring for 6 months followed by RT-CGM use for 6 months

366

367 **D. Duration of Follow-up**

- 368 • RCT outcome at 6 months
- 369 • Subsequent observational study outcome at 1 year
- 370 • Total duration – 1 year

371 **E. Main Outcome Measures**

372 RCT – 1st 6 months

373 Treatment group comparisons of the following:

- 374 • HbA1c
- 375 • Episodes of severe hypoglycemia
- 376 • Percentage of sensor values in range (70 mg/dL to 180 mg/dL)*
- 377 • Biochemical hypoglycemia (percentage of sensor values <70 mg/dL)*
- 378 • Quality of life measures
- 379 • Measures of variability: mean amplitude of glycemic excursions (MAGE), SD, mean absolute
380 rate of change*

381

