619 Enrolled subjects will return 10 (+3) days after enrollment for baseline testing and randomization. The
620 purpose of the visit will include the following:

- 621 • Assessment of compliance with the use of the RT-CGM and HGM
- 622 • Assessment of skin reaction in areas where a RT-CGM sensor was worn
- 623 • Randomization to the RT-CGM Group or the Control Group
- 624 • For subjects in the RT-CGM Group, initiation of unblinded RT-CGM use
- 625 • Instruction on downloading of glucose data for those with a home computer
- 626 • Collection of blood sample to send to the central laboratory for HbA1c determination

627
628 **3.2 Review of RT-CGM and HGM Data**

629 The HGM and RT-CGM data will be downloaded and reviewed by personnel not involved with treatment
630 of the subject to assess whether the subject has been compliant.

- 631 • To be continued in the study, it will be necessary that the subject has completed at least 3 HGM
632 measurements a day since enrollment, has used the RT-CGM on at least 6 out of 7 days prior to
633 the visit, and obtained at least 96 hours of RT-CGM glucose values with at least 24 hours of
634 glucose values during the hours of 10 p.m. and 6 a.m.

635
636 Subjects not meeting these criteria may be given a second opportunity at investigator discretion to
637 complete the RT-CGM and HGM requirements.

638
639 Subjects who are unable to meet the RT-CGM and HGM compliance requirements will be withdrawn
640 from the study and not randomized.

641
642 **3.3 Randomization**

643 Subjects who have been compliant with home glucose monitoring and use of the RT-CGM will be
644 randomized to one of two treatment groups:

- 645 1. RT-CGM Group
- 646 2. Control Group

647
648 The subject's randomization group assignment is determined by entering the Randomization Visit data on
649 the study website.

- 650 • The Jaeb Center will construct a Master Randomization List using a permuted block design.
- 651 • For subjects with baseline HbA1c $\geq 7.0\%$, the randomization will be stratified by clinical center,
652 age (8-<15, 15-<25, ≥ 25) and HbA1c (7.0-8.0, 8.1-10.0).
- 653 • For subjects with baseline HbA1c $< 7.0\%$, the randomization will be stratified by clinical center
654 only.

655
656 *Once a subject is randomized that subject will be included in the data analysis regardless of whether or*
657 *not the protocol for the assigned randomization group is followed. Thus, the investigator must not*

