9.2 Statistical Analysis

9.2.1 Primary Cohort

9.2.1.1 Randomized Trial

Analysis will follow the intent-to-treat principle with all subjects analyzed in the group to which they were randomized, regardless of actual sensor wear. The primary analysis will include all subjects in the primary cohort. Preplanned subgroup analyses will be performed separately for each of the age strata: 8 to <15 years old, 15 to <25 years old, and ≥ 25 years old.

• HbA1c

The primary outcome for this cohort is the HbA1c value at 26 weeks measured in the central laboratory. If the laboratory value is unavailable then the DCA2000 value at 26 weeks will be imputed. If neither measurement is available then the value will be imputed based on available previous lab and/or DCA2000 HbA1c measurements (baseline, 4, 8, 13 and/or 19 weeks) using Rubin's method.¹⁷

Mean \pm SD values for the 26 week HbA1c value with 95% confidence intervals or percentiles appropriate to the distribution will be given for each randomization group. Randomization groups will be compared using an ANCOVA model adjusting for baseline HbA1c and factors used to stratify the randomization. Residual values will be examined for an approximate normal distribution. If values are highly skewed then a transformation or non-parametric methods will be used instead. However, previous experience suggests that HbA1c values will follow an approximate normal distribution. A 95% confidence interval will also be given for the difference of the randomization groups based on the ANCOVA model.

Improvement of at least 0.5% from baseline to 26 weeks will be analyzed as a secondary (binary) outcome. Randomization groups will be compared using logistic regression adjusting for the same factors mentioned above in the ANCOVA model.

• Glycemic Indices

The percentage of sensor values in the target range of 71-180 mg/dL at 13 and 26 weeks (separate outcome measures) will be compared between the two randomization groups (adjusted for the type of RT-CGM that was used). The percentage of sensor values in the hypoglycemic range (≤ 70 mg/dL) also will be compared.

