Percentages of sensor values in the target and hypoglycemic ranges will be calculated giving equal weight to each of the 24 hours of the day for each subject. Comparisons of the two randomization groups will be performed using analogous ANCOVA models as described above for HbA1c. Residual values will be examined for an approximate normal distribution. If values are highly skewed, then a transformation or non-parametric methods will be used instead.

Randomization groups will also be compared for the total amount of sensor data available for this analysis at 13 and 26 weeks, amount of data between 10 p.m. – 6 a.m. and the percentage of subjects requiring a second week of sensor wear.

• Hypoglycemia

Clinical hypoglycemic events will be tabulated in each treatment group, which will be compared using Fisher's exact test. For purposes of analysis, a hypoglycemic event will be defined as an event requiring assistance of another person to actively administer carbohydrate, glucagon, or other resuscitative actions. These episodes may be associated with sufficient neuroglycopenia to induce seizure or coma. If plasma glucose measurements are not available during such an event, neurological recovery attributable to the

1182 restoration of plasma glucose to normal is considered sufficient evidence that the event was induced by a
1183 low plasma glucose concentration.

1184
1185 • **Questionnaires**

1186 Mean \pm SD values or percentiles appropriate to the distribution will be given by randomization group for
1187 the total score and each subscale for each questionnaire at 26 weeks. Results will be given separately for
1188 patient (for those old enough to fill out the questionnaire) and parent responses. For questionnaires
1189 administered to both randomization groups (i.e., excluding the CGM Satisfaction Scale comparisons will
1190 be made using similar ANCOVA models as described above for HbA1c. No formal adjustment will be
1191 made for multiple comparisons.

1192
1193 • **Skin Assessments**

1194 For each scheduled visit and any unscheduled visits during which an assessment was performed
1195 tabulations will be given for percentage of subjects with dry skin, scabbing and scarring and for adverse
1196 events due to skin reaction.

1197
1198 • **Adverse Events**

1199 Adverse events will be tabulated by treatment group and statistical tests performed as appropriate.
1200

1201 **9.2.1.2 Post-RCT Observation Phase**

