1202 Mean \pm SD (or percentiles appropriate to the distribution) HbA1c values will be given by randomization
1203 group at baseline, 13 and 26 weeks of phase 2. The paired t-test will be used to compare the original
1204 control group at baseline vs. 26 weeks of phase 2. A similar t-test will be used to compare the group
1205 originally randomized to the sensor at 26 weeks of phase 2 vs. baseline of phase 1 and vs. baseline of
1206 phase 2 to see if any benefit was sustained through 1 year. Similar analyses will be performed for the
1207 percentage of sensor values in the target and hypoglycemia ranges and questionnaires. The number of
1208 hours of sensor data obtained in the week prior to the 13 and 26 week visits of phase 2 will be tabulated.
1209 Any adverse events will be summarized as described above.

1210
1211 **9.2.2 Secondary Cohort**

1212 Analyses in the secondary cohort (HbA1c $<$ 7.0% at baseline) will parallel those described for the primary
1213 cohort. The percentage of sensor values \leq 70 mg/dL at 26 weeks of phase 1 will be considered the
1214 primary outcome with HbA1c treated as a secondary outcome. Analysis will follow the intent-to-treat
1215 principle with all subjects analyzed in the group to which they were randomized, regardless of actual
1216 sensor wear.

1217
1218 **9.3.3 Cost-effectiveness Analysis**

1219 The cost-effectiveness analysis will be detailed in a separate document and is summarized below.
1220

1221 The analyses will address the following objectives:

- 1222 • To collect utilities for T1D-related health states for patients and their caregivers and to measure
1223 health care utilization and economic consequences attributable to RT-CGM.
 - 1224 • To evaluate the within-trial cost-effectiveness of RT-CGM compared with standard care.
 - 1225 • To evaluate the lifetime cost-effectiveness of RT-CGM utilizing a simulation model of the
1226 complications of diabetes.
 - 1227 • To compare the lifetime cost-effectiveness of RT-CGM with perfect self-selection with lifetime
1228 cost-effectiveness based on traditional cost-effectiveness analysis.
- 1229

1230 For all analyses, the effectiveness parameter will be expressed in terms of quality-adjusted life-years
1231 (QALYS). Cost accounting will vary according to the time-frame and perspective of the analysis. The
1232 within-trial health system perspective will include all the direct costs associated with the program and all

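### The stated covariate rule leaves age group out of the secondary cohort's ANCOVA and insulin modality out of both cohorts' models; validity is unaffected, but some precision may be lost

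*Protocol*

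**What the plan says.** - **Randomization (Protocol 3.3).** Both cohorts use permuted blocks, and for both "the randomization will be stratified by clinical center". The primary cohort adds age group "and HbA1c (7.0-8.0, 8.1-10.0"). The secondary cohort (baseline HbA1c below 7.0%) has center and nothing else.
- **Model (Protocol 9.2.1.1, HbA1c).** Groups are "compared using an ANCOVA model adjusting for baseline HbA1c and factors used to stratify the randomization".
- **Sensor outcomes (Protocol 9.2.1.1, Glycemic Indices).** The target-range comparison is "adjusted for the type of RT-CGM that was used", and the hypoglycemic range is compared as well. These comparisons "will be performed using analogous ANCOVA models as described above for HbA1c".
- **Secondary cohort (Protocol 9.2.2).** "Analyses in the secondary cohort" are to run parallel to the primary cohort's. The primary outcome is the share of sensor values at or below 70 mg/dL at 26 weeks.
- **Composition.** Section 1.6.1 B states: "The secondary study (HbA1c <7.0%) will include a minimum of 120 subjects, with approximately 40" in each of three age groups. Section 9.1.2 pools the analysis over age. Sections 1.6.1 B and 2.1 aim for about half pump users and half injection users.
- **Availability.** Age and insulin regimen are eligibility criteria (section 2.2.1), so both are known for every subject before randomization.

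**The concern.** The covariate list follows from the randomization factors, so it is shortest where the randomization is simplest. The same rule adjusts for age in the primary cohort and not in the secondary cohort, though both are recruited in the same three age groups. Insulin modality appears in no stratification and no model.

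The protocol itself treats both variables as relevant. Section 1.1 reports higher HbA1c and more severe hypoglycemia in intensively treated adolescents than in adults. Section 3.3 stratifies the primary cohort by age. Section 1.3 explains that a second pilot in injection users is under way because the first enrolled pump users only.

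At stake is the width of the confidence interval in the smaller cohort. If either variable predicts the 26-week outcome beyond the baseline value, center and device type, its variation stays in the residual error although the data to remove it are already collected.

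**Working it through.** **Inputs.** Protocol 9.1.2: SD 4.1 points, correlation 0.66, difference 2 points, two-sided 5%, power 90%, 51 per group. Protocol 9.1.1: SD 0.9, correlation 0.58, difference 0.5, 47 per group in each age stratum. The share of residual variance explained by age and modality together (R2) is not in the protocol. It is assumed to be 0.02 to 0.10, with 0.20 shown as an extreme.

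**1. The plan's own figures.** The baseline-adjusted SD is SD x sqrt(1 - r^2).
- Secondary: 4.1 x sqrt(1 - 0.66^2) = 3.080. This needs 50 per group by the normal formula and 51 by the noncentral t. The plan has 51. Then 102/0.85 = 120, as stated.
- Primary: 0.9 x sqrt(1 - 0.58^2) = 0.733. This needs 46 (normal) or 47 (t). The plan has 47.

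Both sample sizes hold with baseline adjustment alone.

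**2. Adding age group (2 df) and modality (1 df) in the secondary cohort.** The residual SD becomes 3.080 x sqrt(1 - R2). Power is for 51 per group by the noncentral t, with three further df spent.

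| Assumed R2 | Residual SD | Power | n per group for 90% |
|---|---|---|---|
| 0 | 3.080 | 90.1% | 51 |
| 0.02 | 3.049 | 90.6% | 50 |
| 0.05 | 3.002 | 91.5% | 49 |
| 0.10 | 2.922 | 92.8% | 46 |
| 0.20 | 2.755 | 95.2% | 41 |

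Center and RT-CGM type are left out of both sides of this comparison, because the plan already includes them.

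**3. A cost the table does not carry.** Three extra covariates that are balanced only by chance also inflate the variance of the treatment estimate, by roughly 3/102 = 2.9%. The net variance ratio is about (1 - R2) x 1.029. At R2 = 0.02 it is 0.98 x 1.029 = 1.01, so no gain. At R2 = 0.10 it is 0.90 x 1.029 = 0.93, so about 7% less variance. The table therefore shows the upper side of the gain, and break-even lies near R2 = 0.03.

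**4. Simulation.** With 10,000 runs, 51 per group and R2 = 0.10, type I error was 4.9% without and 5.1% with the two variables. The simulation error is sqrt(0.05 x 0.95/10,000) = 0.2 points, so these agree. Power was 89.8% without and 92.2% with them: a gain of 2.4 points, against 92.8 - 90.1 = 2.7 in the table.

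**5. Primary cohort.** Age is already in this model, so R2 here is for modality alone. Within one age stratum (47 per group), power goes from 90.5% to 91.0% at R2 = 0.02 and 93.1% at R2 = 0.10, still charging three df, which is more than modality needs. The pooled analysis, with 3 x 47 = 141 per group after losses, already has power above 99.9% for a difference of 0.5.

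**The case against.** The strongest reply is that nothing here is an error. Adjusting for baseline and every stratification factor is a coherent, standard rule. The sample sizes do not depend on further covariates, a recruitment target need not be a covariate, and the secondary cohort is described as a pilot (section 1.6). Chapter 9 also calls itself a synopsis that the later analysis plan will supersede. This all stands, and it limits the point to a suggestion. It does not remove the point, because the protocol states a covariate rule rather than leaving the list open.

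It can also be said that age carries over because section 9.2.2 makes the secondary analyses parallel the primary ones, whose model contains age. That reading is possible. But the rule refers to the factors used to stratify, and in this cohort age is not one of them. One sentence in the plan would settle it.

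A reader might infer three stronger things that the protocol does not support:
- **That the secondary model contains only baseline and center.** Its primary outcome is a sensor percentage. The adjustment for RT-CGM type is attached to the target-range sentence, but most naturally reaches the hypoglycemic range too.
- **That chance imbalance biases the comparison.** Under randomization such imbalance is already reflected in the standard error, and the simulated type I error is the same with and without the covariates.
- **That age is balanced no better than by simple randomization.** Allocation is blocked within center, and section 2.1 expects some centers to enroll only children or only adults. Blocking on center and adjusting for it therefore control part of age. Nothing comparable is stated for modality.

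**Conclusion.** The point holds as a minor one about precision. On its plain reading the rule gives the secondary cohort a model with baseline, center and RT-CGM type but not age group, and neither cohort's model contains insulin modality. Type I error and the stated sample sizes are not affected.

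If the two variables explain 2 to 10% of the residual variance, secondary-cohort power rises from 90.1% to about 90.6-92.8%, or by 0.5 to 2.7 points. With the cost of chance imbalance included, the lower end is effectively zero. The result rests on that assumed R2. Baseline adjustment already absorbs any effect of age or modality that is present in the baseline value, and center absorbs part of age, so the true figure could be at or below the low end. In the pooled primary analysis the gain is negligible; modality would mainly help the separate age-stratum analyses.

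**What to change.** For the secondary cohort, pre-specify age group (three levels) and pump versus injections as ANCOVA covariates, in addition to baseline, center and RT-CGM type. State explicitly that the RT-CGM-type adjustment applies to the outcome at or below 70 mg/dL. In the primary cohort, adding modality is optional, chiefly for the age-stratum analyses. Fix the list in the analysis plan before outcome data by group are seen.

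The cost is about three degrees of freedom in the secondary cohort and one in the primary, plus the small variance cost shown above if the variables turn out to predict little. No new data, change to the randomization or change to the sample size is needed.

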4.1 Home Procedures and Diabetes Management

4.1.1 RT-CGM Group

Each subject will be asked to use a RT-CGM sensor on a daily basis, inserting a new sensor as needed.

A study HGM will be used for calibration of the RT-CGM sensor. Additional HGM glucose measurements may be performed by the subject at anytime, particularly prior to making a real-time management decision based on the RT-CGM glucose reading.

At least once a week, subjects who have a home computer will be instructed to download the RT-CGM and HGM data for viewing. Subjects with email access will send the RT-CGM and HGM data to the clinical center prior to each scheduled phone call. The steps to follow will be detailed in the subject instruction manual.

Subjects who are not successfully using the assigned RT-CGM may be switched to a different RT-CGM if more than one is in use in the study. Criteria to be used in deciding whether a switch is to be made will be provided in the site procedures manual.

4.1.2 Control Group

A study HGM will be used for a fingerstick blood glucose check a minimum of four times a day (prior to each meal and bedtime). Subjects will be permitted to check a fingerstick glucose as many times a day as they choose.

Subjects who have a home computer will be asked to download the HGM at least once a week. Data summaries and charts will be available for these subjects to view. Subjects with email access will send the HGM data to the clinical center prior to each scheduled phone call. The steps to follow will be detailed in the subject instruction manual.

